## Methods

### Study Design

This study will be broken down into a pilot phase, followed by two stages of data collection. We will recruit, consent, and enroll approximately 2050 participants with a COVID-19 positive test over the course of the study. In the pilot phase and stages one and two, the following methods will apply.

Participants will be asked to wear the Current Health remote patient monitoring device for up to 30 days. Participants will also be provided with a Current Health tablet with an application installed. The tablet is not password protected, but no responses are stored locally, and they are associated with vital signs via the Current Health dashboard. The participant will be asked to complete a welcome survey on the first day of participation. The tablet will remind the participant each day to answer a brief series of questions about their symptoms and decisions on the tablet. The welcome and daily surveys include the content below:

Welcome Survey: Welcome! Today is your first day in Community by Current Health's COVID-19 Study. We need to collect some information about you. We will only ask these questions **one time**. This survey should take **less than 5 minutes to complete**.

Thank you again for taking part in this study. With your help our researchers will gain a better understanding of COVID-19 and be able to predict recovery and progression.

- 1) What is your date of birth?
- 2) What is your sex? Male/Female/other or prefer not to specify

If Female

- 1) To your own knowledge are you currently pregnant?
- 2) Do you have menstrual periods?
- 3) Are you:
  - Pregnant or breastfeeding
  - Taking hormonal birth control
  - Undergoing menopause or post-menopausal - Highly active (working out, training, fitness, etc.)
- 4) When was your last period?
- 3) What is your occupational category? Healthcare (doctor, nurse, dentist, etc.)  
Service industry (food service, grocery, mechanic, plumber, etc.)  
Retail  
Office – able to work from home  
Office – unable to work from home  
Currently unemployed  
Student – remote  
Student – attending class in person
- 4) What is your household make-up?  
Living alone  
Living with people
- 5) Do other members of your household currently have COVID-19? Y/N
- 6) Are any other members of your household enrolled in Community by Current Health's COVID-10 Study? Y/N
- 7) What is your self-identified race/ethnicity?  
White Hispanic

White Non-Hispanic  
 Black or African American  
 Asian  

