 American Indian or Alaska Native  
 Native Hawaiian and Pacific Islander 8)

What is your height?

9) What is your weight (in pounds)?

10) Do you have **asthma**? Y/N

11) Do you have **cancer**? Y/N

12) Do you have **chronic obstructive pulmonary disease (COPD)**? Y/N

13) Do you have **diabetes**? Y/N

14) Do you have a **heart condition**? Y/N

15) Do you have **high blood pressure**? Y/N

16) Do you have **kidney disease** or **reduced kidney function**? Y/N

17) Have you ever had an **organ transplant**? Y/N

18) Do you have **sickle cell disease**? Y/N

19) Are you a **smoker**? Y/N

20) Do you take **beta blockers**? Beta blockers are medicines designed to reduce heart rate, which can affect vital sign readings. For example: Tenormin, Cardiacor, Emcor, Betaloc, Inderal, or Angilol.  
 Y/N

21) Please enter any feedback about this survey:

Thank you for filling out your welcome survey! Your responses have been recorded.

Daily Survey:

Each day Current Health will ask you a **brief series of questions** about symptoms and decisions that may be related to COVID-19. Your daily response and information collected from the wearable device will create the most accurate picture of your health. This survey should take **less than 5 minutes** to complete.

1) In the **past 24 hours**, did you have (or continue to have) any of the following symptoms:

- ✦ loss of smell or taste
- ✦ dry cough
- ✦ sore throat
- ✦ fever or feeling feverish
- ✦ chills
- ✦ muscle aches
- ✦ diarrhea
- ✦ nausea
- ✦ other, please specify (free text)

[FOR EACH YES] Is your <symptom> better or worse than yesterday?

- ✦ Categorical scale: Much worse, Worse, The same, Better, Much better

- 2) Due to how you are feeling **today**, do you plan to speak to a health care provider?
- 3) Due to how you are feeling **today**, do you plan to go to the hospital?
- 4) Do you feel as though you have completely recovered from COVID-19 as of today?

Thank you for completing your daily survey! Your responses have been recorded.

For our study participants, data will be collected “blind”. The participant will not be able to see their data in real time, and no data will be reviewed or acted upon by the study team unless there is a clinically indicated trigger elicited by the system. These triggers exist to prompt the capture of study-specific information, not to direct patient care.

1. Reduction in SpO2 below 88% for 60 minutes

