## **Stage 2**

### *Testing Stage – Expansion for Model Creation or Validation*

To assess the algorithm performance, algorithm testing on a total of 1,000 participants will be conducted. This cohort of 1,000 testing participants will be held entirely separate from the

training participants to minimize data snooping bias in the study. In machine learning, it is typical to obtain initial testing cohort results to determine if the model created from the training data is performing well. After the first 100 participants in the testing cohort are monitored for 30 days, the algorithm will be tested for understanding initial performance. As more participants are recruited into the study, follow-up algorithm testing will occur for each 100 participants that are added to the testing cohort.

Although the outcome of the participants in the validation set is known, the outcomes will be initially ignored, as if researchers did not know participant outcome. This simulates what researchers know about a participant, preceding the participant's outcome. The testing participants' collected variables (demographic, medical history, continuous data from wearable, and symptom data) will be run through the developed Bayes network algorithm and comparison models. The algorithm will return probabilities of the study outcomes. The algorithm's probabilities will then be compared with the true outcome of the participant recorded by the study team.

The differences between the algorithm prediction and participant's true outcome will be used to calculate performance metrics such as positive predictive value (PPV), area under the curve/receiver operating characteristic (AUC/ROC), and Brier scores. The final part of algorithm validation will be calibration analysis, sensitivity analysis, and determining any subpopulations that may have had poor predictive performance.

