**Table 2. Variables collected for analysis**

Table 2. Variables collected for analysis	
Continuously acquired variables	Categorical variables (continued)
1. Respiration rate	13. Age
2. Pulse rate	14. Sex
3. Oxygen saturation	15. Occupation
4. Skin temperature	16. Household make-up (living alone or with people)
5. Step count	17. Other household members with COVID19
6. Activity levels	18. Other household members enrolled in this study
Categorical variables	19. Menopausal state and time since last menstrual cycle / Pregnancy status
7. Symptoms	20. Race/Ethnicity
8. Days when reporting for employment	21. Zip code
9. Outcomes of any SARS-CoV-2/COVID-19 testing	22. BMI (height & weight)
10. Admission to hospital, ICU, death	23. Comorbidities
	24. Acute and Chronic Medication

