## 8. Trial Population

### 8.1. Recruitment and Screening

Participant recruitment will primarily use social media (Facebook) and internet advertisements. The study population may contain biases such as a younger audience and those “tech savvy” enough to wear a medical device for the duration of the study compared to the general population. These potential limitations will be considered in the study’s scope of generalizability. For screening, participants who are more likely to fit inclusion criteria could be correlated with other social determinants of health, which will also be in the study’s scope of generalizability. Where population demographic information deviates far from the general population expected this will be highlighted.

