### Inclusion and Exclusion Criteria

**Table 1. Criteria for study participants**

Inclusion	Exclusion

 
1. Living in the United States
 
2. Aged 21 years or older
 
3. Able to provide documentation of +PCR or +antigen test for COVID-19 within the past 48 hours
 
4. Self-reports that comfortable and willing to wear the wearable device and interact with a tablet-based interface daily
 
5. Able to provide a next of kin/designated person who can be contacted in the event of hospitalization for follow up.
 
	
 
1. Under the age of 21
 
2. Received a positive test result more than 48 hours prior to contacting study staff or has a pending test for COVID-19
 
3. Cannot confirm a PCR or antigen positive test for COVID-19.
 
4. Is unable to read English
 
5. Is unwilling to wear the device 24 hours/day except for showering/bathing or interact with a tablet-based interface for daily questionnaire
 
6. Is unwilling or unable to provide baseline data required for entry into the study
 
7. Is unable to provide a next of kin/designated person who can be contacted in the event of hospitalization for follow-up
 
8. Heavy tattooing on both upper arms
 
9. Known atrial fibrillation (permanent or paroxysmal)
 
10. Has taken/is taking part in a COVID19 vaccine or treatment study
 

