## 8.5. Baseline Participant Characteristics

Characteristics will be presented in a descriptive summary table — continuous variables as mean and standard deviation or median and quartiles, and categorical and binary variables as absolute and relative frequencies. The analysis population will be produced for those who complete the trial to a study outcome including recovery. Surveys will be administered via tablet, which is part of the CH device kit a participant receives. The list of baseline participant characteristics and description of how they will be recorded are captured in the following table. The variables planned to be captured represent the most recent literature findings of COVID-19 risk factors.

Description	Variable	Variable Type
*Participant Intake Survey		
Date of birth	dob	Date (MMDDYYYY)
Sex	sex	Categorical: Male, Female, Other or prefer not to specify
Pregnant	pregnant	Binary: Yes, No
Presence of menstrual periods	menstrual_periods	Binary: Yes, No
Absence of menstrual periods reason	no_periods_reason	Categorical: Pregnant or breastfeeding, Taking hormonal birth control, Undergoing menopause or post-menopausal, High active, Other
Date of last period	last_period	Date (MMDDYYYY)
Occupational category	occupational_cat	Categorical: Healthcare, Service industry, Retail, Office - able to work from home, Office - unable to work from home, Currently unemployed, Student - remote, Student - attending class in person
Household make-up	household_makeup	Binary: Living alone, Living with people
Do other members of your household currently have COVID-19?	household_covid	Binary: Yes, No

Are any other members of your household enrolled in Current Health's COVID-19 study?	household_study	Binary: Yes, No
What is your self-identified race/ethnicity?	race_ethnicity	Categorical: White Hispanic, White Non-Hispanic, Black or African American, Asian, American Indian or Alaska Native, Native Hawaiian and Pacific Islander
Height	height	Discrete (user input)
Weight (in pounds)	weight	Continuous: (pounds or kg user input)
Asthma	asthma	Binary: Yes, No
Cancer	cancer	Binary: Yes, No
Chronic obstructive pulmonary disease (COPD)	copd	Binary: Yes, No
Diabetes	diabetes	Binary: Yes, No
Heart condition	heart_condition	Binary: Yes, No
High blood pressure	hbp	Binary: Yes, No
Kidney disease or reduced kidney function	kidney_disease	Binary: Yes, No
Organ transplant	organ_transplant	Binary: Yes, No
Sickle cell disease	sickle_cell_disease	Binary: Yes, No

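### The one race/ethnicity item records Hispanic ethnicity only as White Hispanic and has no multiple, other or decline option, so results cannot be reported for Hispanic participants as a whole

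*Combined protocol and SAP*

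**What the plan says.** The Welcome Survey in the protocol (Study Design, item 7) asks "What is your self-identified race/ethnicity" and lists six options. SAP 8.5 stores the answer in a single variable, race_ethnicity, with the same six values: "Categorical: White Hispanic, White Non-Hispanic, Black or African American, Asian, American Indian or Alaska Native, Native Hawaiian and Pacific Islander". In the same SAP table, sex is coded "Categorical: Male, Female, Other or prefer not to specify", so an escape option was thought of for one demographic item but not for the other.

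The plan uses this variable, or could use it, in three places:

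- Protocol Table 2 lists "20. Race/Ethnicity" among the variables collected for analysis. It is therefore a candidate for the Bayesian network.
- Protocol Stage 2 ends the validation with several checks, one of which is "determining any subpopulations that may have had poor predictive performance".
- SAP 8.1 says of the recruited sample: "Where population demographic information deviates far from the general population expected this will be highlighted".

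**The concern.** Race and ethnicity are merged into one item, and Hispanic is separated from non-Hispanic only among White participants. A Black, Asian, American Indian or Pacific Islander participant who is Hispanic has no matching option. Nor has someone of another race, someone who prefers not to answer or, under single choice, someone of more than one race.

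Three things are at stake. The Hispanic share is a basic description of a sample recruited largely through social media, and it could not be stated. A model that is to be deployed if it meets its benchmark could not be shown to work, or to fail, in Hispanic participants taken together. A candidate predictor would also carry avoidable misclassification or missing values. SAP 10 bases percentages on non-missing answers, so people who skip the item would drop out of the denominator.

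**Working it through.** The plan states no figure on this point, so there is none to reproduce. The check sets the passages side by side and then sizes the gap under stated assumptions.

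**1. Do protocol and SAP agree?** Yes. Both list the same six options in the same order. The gap is therefore not an abbreviation in one document or a fault of text extraction.

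**2. Does another field fill the gap?** No. The only free text in the intake survey asks for feedback on the survey. Zip code (SAP 8.7) is meant for area-level social determinants. Neither document has a separate ethnicity item.

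**3. What can be recovered?** Let H be the number of Hispanic participants and W the number who choose White Hispanic. If only Hispanic participants choose that option, W ≤ H. The other H − W people are spread over the non-Hispanic categories or are blank, and nothing in the data gives their number. W is thus a lower bound for H with an unknown shortfall. W may also include Hispanic participants of another or mixed race who took the only Hispanic option offered.

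**4. Size.** Inputs from the documents are 1,000 participants per cohort and an event rate of about 10% (SAP 6.3), hence about 100 events. The shares are assumptions.

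- If 2% to 10% fit no option: 0.02 × 1,000 = 20 to 0.10 × 1,000 = 100 people. At 10%, that is 2 to 10 events.
- The table takes a Hispanic share of 10% or 20%, of whom 50% to 75% choose White Hispanic. Half-widths are for a 95% interval around an AUC of 0.75, using the Hanley-McNeil standard error: SE² = [A(1 − A) + (n₁ − 1)(a − A²) + (n₀ − 1)(b − A²)] / (n₁n₀), with a = A/(2 − A) = 0.600 and b = 2A²/(1 + A) = 0.643. Here n₁ is events and n₀ is non-events.

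| Assumed Hispanic share | All Hispanic: people, events, half-width | Recorded as White Hispanic: people, events, half-width | Not identifiable |
|---|---|---|---|
| 10% | 100, 10, 0.18 | 50 to 75, 5 to 7.5, 0.26 to 0.21 | 25 to 50 people |
| 20% | 200, 20, 0.13 | 100 to 150, 10 to 15, 0.18 to 0.15 | 50 to 100 people |

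One cell in full, for 20 events and 180 non-events: SE² = (0.1875 + 19 × 0.0375 + 179 × 0.0804) / 3,600 = 0.00425, so SE = 0.065 and 1.96 × SE = 0.13.

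- A multiracial share of 2% to 5% would give 20 to 50 people and 2 to 5 events, with a half-width of about 0.41 to 0.26. Under single choice none of them is identifiable.

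**The case against.** The case on the other side has real force.

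- **The planned check is not blocked.** A reader might infer that the Stage 2 subpopulation check cannot be done for Hispanic participants. The documents do not support that. White Hispanic is a recorded category and can be assessed. The check names no subgroup, metric or threshold, and the SAP's Stage 2 text does not repeat it. It can be run on every recorded category. This stands.
- **Single choice is inferred.** Neither document says whether the item is single-choice or tick-all. One categorical variable with one value list implies single choice. If it were tick-all, multiracial participants could be identified, but the other and decline options and a clean record of Hispanic ethnicity would still be missing.
- **The gap can be repaired for a time.** A reader might infer that the loss is permanent because the survey is given once. But the linking key is destroyed only when data analysis ends (protocol, Data Management & Security), and staff contacts run to Day 30, with outcome verification possible for 30 days more (SAP 6.6).
- **Skipping is not shown to cost eligibility.** The exclusion "Is unwilling or unable to provide baseline data required for entry into the study" does not say which data are required, and SAP 6.6 places the intake survey after the kit arrives.
- **Race/ethnicity is only a candidate.** The protocol's section on the algorithmic approach lets variables be dropped or re-binned.
- **Precision is poor either way.** With a handful of events, a subgroup AUC says little even with a perfect form. This stands too, most of all for multiracial participants. Still, a wide interval can be reported and combined with later data, whereas an uncollected answer cannot.

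**Conclusion.** The point holds as a limited data-capture gap; the label is cheap improvement. As written, the Hispanic share cannot be computed. Performance cannot be reported for Hispanic participants as a whole or, on the reading that the item is single-choice, for multiracial participants. Some participants will be misfiled or blank on a candidate predictor.

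The size is not known from the documents. The 20 to 100 people per cohort, and the figures in the table, rest on assumed shares and on the plan's 10% event rate applying equally in each group. The primary analysis, the sample size and the AUC criterion do not change.

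**What to change.** Replace Welcome Survey item 7 with two items: (a) Hispanic or Latino: Yes / No / Prefer not to say; (b) race: tick all that apply, adding Other and Prefer not to say. Replace race_ethnicity in SAP 8.5 with the matching variables. In the Stage 2 text of SAP 9.2, name both as subgroups for the performance check, reported with intervals and event counts. Report the number missing or declined alongside the percentages. For anyone already enrolled, ask both questions during routine study contacts while the linking key exists.

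The cost is one more question, a form amendment with ethics board notification and, if enrolment has started, harmonising two codings. Sparse categories must be merged before modelling. Counted as regression-type parameters, six exclusive categories use 6 − 1 = 5, whereas one ethnicity indicator plus up to six race indicators (the five races now listed and Other) use 1 + 6 = 7. Protocol Appendix B already assumes 30 parameters, the ceiling of its formula. The pilot, which is meant to uncover user issues that affect the data, is a natural point for the change.

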## 8.6. Continuous Vital Signs

Continuous vital signs are as follows and are reported as continuous and discrete data:

Variable	Variable Type
Respiration rate	Continuous numeric
Respiration rate	Continuous numeric
Pulse rate	Continuous numeric
Oxygen saturation	Continuous numeric
Skin temperature	Continuous numeric
Step count	Discrete numeric
Activity levels	Discrete numeric

## 8.7. Derived Variables

In order for CH to ship a kit to a participant zip code will be collected. Zip code may be used during analysis to determine potential social determinants of health such as median household

income in an area. BMI will be derived from height and weight measurements. Date of birth will be used to calculate age and age may be used to derive age groups.

## 9. Analysis

### 9.1. Outcome definitions

Study outcomes will be ascertained by the CRA within the study observational period of 30 days or the following 30 days if the participant has not definitively experienced other outcomes of recovery or death.

Primary and secondary outcomes are presented in (5.1) and will be presented as follows.

Description	Variable	Variable Type
Recovery from COVID-19	recovered	Binary: Yes, No
Hospital stay of 24 hours or longer	hospitalized	Binary: Yes, No
ICU admission	icu_admission	Binary: Yes, No
Death	death	Binary: Yes, No

No calculations are necessary to derive primary or secondary outcomes, they all will be directly stated in binary terms.

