## Research Objective and Outcomes

The overall objective of this contract is to train, develop, validate and release a digital biomarker-based algorithm that, in COVID-19 PCR or antigen positive patients, within 30 days of a positive test:

1. **Primary Outcome:** predicts likelihood of requiring a stay in hospital of 24 hours or longer
2. **Secondary Outcomes:**
  - a. Predicts likelihood of being admitted to ICU for either non-invasive (CPAP, BiPAP, high flow nasal oxygen), invasive ventilation or vasopressor support.
  - b. Predicts likelihood of death.
3. **Tertiary Outcomes:** Provides successful delivery, setup, daily interface engagement, and compliance with wearing of the device

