## Recruitment Strategies

The primary recruitment tactics will involve digital marketing through social media (Facebook Advertising), and Google Advertising. We will use CDC data to target areas experiencing outbreaks of SARS-CoV-2/COVID-19. Additional recruitment tactics include email content and circulation of physical materials such as flyers, posters, or bulletin boards and direct mailers. All marketing material will direct to the website, including study team contact information, for initial screening. Throughout the enrollment process, Current Health will communicate updates on the clinical trial and/or enrolment process via phone calls, text messages, or emails. All materials will be developed by Current Health, reviewed by BARDA funders, and approved by the Advarra Institutional Review Board before becoming patientfacing. No communications via email or text message will contain protected health information.

We plan to create a website to serve as the primary communication method with participants prior to enrollment in the clinical trial. This website (<https://community.currenthealth.com>) sits as a subdomain on the Current Health corporate website, which is secure and HIPAA compliant. We have included the website wording, and sample screenshots as appendices.

On the website, we articulate:

- The goals of the clinical trials
- Qualification criteria for participants
- What is expected of participants as part of the clinical trial
- What compensation the participant can expect to receive
- Support contact information for participants enrolled in the clinical trial

- Information regarding Current Health

Once participants have progressed through the website, their details will be passed to a study team member. The study team member will contact the participant via email or text message and send a copy of the Informed Consent Form. The study team member and participant will arrange a mutually convenient time to speak via telephone or Zoom. Together, they will review the Informed Consent Form and engage with the process of consent. Once consent has been obtained via secure electronic means, the participant will be shipped a Current Health device by a logistics partner (Seko).

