# 5. Study Objectives and Endpoints and Hypotheses

## 5.1. Study Objectives, Endpoints, and Outcomes

The overall objective of this study is to train, develop, validate and release a digital biomarker-based algorithm that, in COVID-19 PCR or antigen positive participants, within 30 days of a positive test:

1. Primary Outcomes:
  - a. Predicts likelihood of requiring a stay in hospital of at least 24 hours
  - b. Predicts likelihood of recovery from COVID-19 defined as:
    - i. For asymptomatic participants: 14 days without symptoms following positive test
    - ii. For symptomatic: at least 14 days since onset of symptoms, with the last three days symptom free
2. Secondary Outcomes:
  - a. Predicts likelihood of being admitted to ICU for either non-invasive (CPAP, BiPAP, high flow nasal oxygen), invasive ventilation or vasopressor support.
  - b. Predicts likelihood of death.
3. Tertiary Outcomes: Successful delivery, setup, daily interface engagement, and compliance with wearing of the device

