## 6.6. Timing of Outcome Assessments

The frequency and timing of all the relevant study assessments is considered from the time the participant CH kit arrives to 30 days of observation or a met outcome.

Study Task	Timeline
Kit Setup	Day 1
Participant Intake Survey	Day 1 to Day 3
*Daily Survey	Daily
CRA Adherence Checks	Day 1 to Day 30 ongoing
Vital signs captured by CH wearable	Day 1 to Day 30 ongoing
Outcome Verification	Day 1 to Day 30 ongoing and 30 days after observation period ends

\*Daily symptom questionnaire will close if not completed within a given number of hours. Participant will still be able to fill out the following day's daily symptom questionnaire.

Variables collected from study assessments will be generally as follows:

- Demographic – Categorical
- Medical history and medication – Boolean
- Symptom presence – Boolean (“Much better” to “Much worse”)
- Symptom severity – Ordinal categorical

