### 7.3. Adherence and Protocol Deviations

A study participant will be considered fully adherent to study protocol if they:

- Wear the CH device for at least 20 hours a day, at least 6 days a week;
- Answer the questions on the tablet at least 6 days a week;
- Return wearable kit and device.

Adherence metrics will be presented in absolute and percentage terms. Both measures will account for how long a participant is in the study. For example, a participant that is observed the entire 30 days will have a possible total of 720 hours (30 days x 24 hours) and 30 answered tablet symptom surveys. This participant's minimum adherence level would be 600 hours of device wear and at least 26 completed symptom surveys. A participant that meets an outcome much earlier due to hospitalization after 7 days would still be considered adherent if prior to hospitalization they wore the device 140 hours and completed 6 symptom surveys.

A summary table will generally be presented with the following variables per participant:

Participant ID
Time in trial (hours)
Hours of CH device observation
Wearable adherence percentage
Time in trial (days)
Number of surveys completed
Survey adherence percentage
Overall study adherence (Y/N)

Following collection all participants this information will be aggregated to the CONSORT flow chart metrics.

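### SAP 9.1 extends the outcome search by 30 days only for unrecovered participants, SAP 6.6 for everyone, and neither says how an event after the SAP 5.1 window is coded

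*Combined protocol and SAP*

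**What the plan says.** **Definition.** The protocol (Research Objective and Outcomes) sets its outcomes "in COVID-19 PCR or antigen positive patients, within 30 days of a positive test". SAP 5.1 does the same: "in COVID-19 PCR or antigen positive participants, within 30 days of a positive test". SAP 5.1 also makes recovery an outcome. For symptomatic participants it means "at least 14 days since onset of symptoms, with the last three days symptom free".

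**Schedule.** SAP 6.6 times assessments "from the time the participant CH kit arrives to 30 days of observation or a met outcome". Its table places outcome verification throughout days 1 to 30 and also "30 days after observation period ends", for all participants. The protocol (Recruitment Strategies) says that after consent "the participant will be shipped a Current Health device by a logistics partner".

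**Ascertainment.** SAP 9.1 covers the 30-day observation period, "or the following 30 days if the participant has not definitively experienced other outcomes of recovery or death". It refers to 5.1 for the list of outcomes, shows each as a yes/no variable, and adds that nothing has to be calculated to obtain them.

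**Event timing in practice.** The adherence rule in SAP 7.3 uses the example "A participant that meets an outcome much earlier due to hospitalization after 7 days", so the study team appears to know when an admission occurred. The SAP 9.1 outcome table has no date variable.

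**The concern.** The hospitalization flag is the label on which the Bayesian network is trained and tested. SAP 5.2 makes its prediction the acceptance criterion (75%), and deployment depends on that criterion. Such a label should be sought equally hard, over the same period, in every participant.

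Under SAP 9.1 the length of the search depends on recovery. For symptomatic participants recovery depends on symptoms having stopped, and SAP 9.2 (Stage 2) lists symptom data among the model inputs. If admissions are sought for longer in people whose symptoms persist, part of any association between symptoms and hospitalization can come from follow-up rather than from disease. The model would learn that part in Stage 1 and be credited for it in Stage 2.

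The SAP 6.6 table does not have this feature, so two teams following different sections could build different labels from the same participants.

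**Working it through.** **1. The plan's own event figure.** SAP 6.3 expects 1,000 × 0.10 = 100 events per cohort, which reproduces. The 10% is described as the share who eventually develop severe disease. It carries no time limit, so it cannot show how many of the 100 fall inside or outside a 30-day window.

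**2. The windows on one clock.** Count days from the positive test and let L be the time from test to kit arrival. The documents do not give L, so it stays a symbol.

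| Source | Starts | Ends | Applies to |
|---|---|---|---|
| Protocol objective; SAP 5.1 | day 0 | day 30 | everyone |
| SAP 6.6, observation | day L | day L + 30, or a met outcome | everyone |
| SAP 6.6 table, second 30 days | day L + 30 | day L + 60 | everyone |
| SAP 9.1, second 30 days | day L + 30 | day L + 60 | only those without definite recovery or death |

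The last row takes the SAP 9.1 observation period to be the one in 6.6. Entry needs a documented positive result and the kit is shipped only after consent, so the first two rows do not share a start. The first L days of the 5.1 window precede monitoring. The last L days of observation, and all of the second 30 days, lie beyond the 5.1 window.

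**3. Search time by recovery status.**
- SAP 9.1, not recovered: 30 + 30 = 60 days at most.
- SAP 9.1, recovered: 30 days.
- Ratio under SAP 9.1: 60 / 30 = 2 at most.
- SAP 6.6 table, either group: 30 + 30 = 60 days, a ratio of 1.

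The 6.6 entry could also mean one check 30 days later rather than a 30-day span. It would still be unconditional, so it would still differ from 9.1.

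**4. Is there a counting rule?** SAP 5.1 states the window. SAP 9.1 names 5.1 as the place where the outcomes are presented, then records each as yes or no without applying a date. No sentence in the text available says whether an admission first occurring in the second 30 days is coded Yes, coded No or set aside. SAP section 12 mentions a section 9.5 and material on temporal data that the text available does not contain, so this absence is established only for what could be read.

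**5. Early leavers.** The protocol (Study Design) lets participants who consider themselves recovered exit and counts them as fully compliant. SAP 9.1 still calls for ascertainment over the first 30 days, but nothing says how their status is coded if it was not confirmed to day 30.

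**The case against.** The best defence is that the window is already fixed. SAP 5.1 defines the outcomes with a 30-day limit and SAP 9.1 refers back to it, which is ordinary drafting. SAP 6.6 is a schedule of assessments, most of which need the kit, so its different start need not create a rival outcome window. The row for the second 30 days is headed as outcome verification, which suggests late confirmation of earlier events. A summary table that omits a condition given in the text is a small editing fault.

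Much of this stands. The window is stated, and the late-confirmation reading is reasonable. A reader might infer that the plan intends to count admissions up to 60 days as primary events. The documents do not say so.

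The defence does not remove the point. SAP 9.1 ties the extension to recovery and death, not to whether an event still needs confirming. Even if the second period is for verification only, under 9.1 just the unrecovered receive it, so an in-window admission that was missed is more likely to be found in them than in the recovered.

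It is also fair that anchoring the outcome at kit arrival would be coherent, since a label fixed at day 30 after the test leaves only 30 − L monitored days. That would, however, change the definition that the protocol and SAP 5.1 share. Keeping the sponsor's own definition is the smaller change.

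**Conclusion.** The point holds in a limited form. SAP 6.6 and 9.1 disagree on who is followed in the second 30 days, and the text available does not say how an event found then is coded against the 5.1 window. If 9.1 is followed as written, search time for the label can differ by up to 2 to 1 according to recovery status, which rests on symptoms that also enter the model. That ratio is a ceiling on calendar time under 9.1 alone. It is not a misclassification rate.

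Three stronger conclusions may tempt a reader, and the documents do not support them:
- **That the reported AUC will be inflated.** The documents give no distribution of admission times, no number unrecovered at day 30 and no number of early leavers. Neither the size nor the direction of an effect on event rate, calibration or AUC can be computed.
- **That the gap between the two clocks can be put in days.** Shipping time is not stated, and the 48-hour eligibility limit runs from receipt of the result, not from the test.
- **That interim tests on labels still open would distort the result.** SAP 9.2 reports only the most recent metrics, which largely answers this.

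The conclusion assumes that the SAP material missing from the text available contains no counting rule.

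**What to change.** In SAP 6.6 and 9.1:
- Derive hospitalization (stay of at least 24 hours), ICU admission and death from event dates within the 5.1 window, positive test to day 30, for every participant whatever their recovery status.
- Use the second 30 days only to verify events dated inside that window, under the same rule for all participants. Report later events separately.
- Make the 6.6 table and the 9.1 sentence agree on who is followed.
- Confirm the day-30 status of participants who exit early, through the participant or the designated contact already required for entry. Code unconfirmed status as missing, not as No.
- Report admissions that occur before any monitoring data exist separately from model scoring.

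The cost is revised wording, event dates carried into the outcome dataset and a brief extra contact for early leavers. The main downside is possibly fewer counted events than the 100 per cohort on which the plan relies.
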